3.1 Primary Objective

Median reduction in monthly convulsive seizure frequency

3.2 Secondary Objectives

- Caregiver/Investigator Global Impression of Change (C/IGIC). The parent/caregiver and investigator rated change on a 7-point scale: 1-very much improved; 2-much improved;
 3-minimally improved; 4-no change; 5-minimally worse; 6-much worse; and 7-very much worse
- Quality of Life in Childhood Epilepsy Scale . A low-burden parent/caregiver completed assessment that looks at how epilepsy affects day-to-day functioning of their child in

Version: 11 Jan 2021

various life areas, including physical activities, well-being, cognition, social activities, behavior and general health in comparison to other children their age,

 PEDS-QL. A parent/caregiver completed assessment that looks at how epilepsy affects day-to-day functioning of their child in various life areas, including physical activities, well-being, cognition, social activities, behavior and general health during a specific time frame.

4. Study Design and Endpoints

4.1 Description of Study Design

The study to be conducted is an expanded access program for intermediate size population use.

4.2 Study Endpoints

4.2.1 Primary Study Endpoints

Median reduction in monthly convulsive seizure frequency. For continuation after initial study period, patients must have a $\geq 40\%$ reduction in convulsive seizure frequency over baseline.

4.2.2 Secondary Study Endpoints

Evaluate changes from Baseline in cognitive, motor, and behavioral function as well as QOL following fenfluramine treatment.

4.2.3 Safety Endpoints

The safety endpoints the study are:

- Adverse events
- Laboratory safety (hematology, chemistry, coagulation, urinalysis)
- Vital signs (blood pressure, heart rate, temperature, and respiratory rate)
- Physical examination
- Neurological examination
- Questionnaires to measure changes in cognition of the subject
- 12-lead ECGs
- Doppler ECHOs
- Body weight

5. Study Enrollment and Withdrawal

All subjects and/or their parent/legal guardian must sign the appropriate informed consent prior to beginning any study-related activities, including Screening procedures. Additionally, an assent form should be signed by subjects age 7 to 17 years old, unless lacking capacity.

5.1 Inclusion Criteria

In order to be eligible to participate in this study, an individual must meet all of the following criteria:

1. Confirmed clinical/genetic diagnosis of CDKL5 Deficiency Disorder CDD

Version: 11 Jan 2021

Ages 2-35 years old. Subject is male or non-pregnant, non-lactating female. Female subjects of childbearing potential must not be pregnant or breast-feeding. Female subjects of childbearing potential must have a negative urine pregnancy test. Subjects of childbearing or child-fathering potential must be willing to use medically acceptable forms of birth control, which includes abstinence, while being treated on this study and for 30 days after the last dose of study drug.

- 3. Subject has been informed of the nature of the study and informed consent has been obtained from the legally responsible parent/guardian.
- Subject has provided assent in accordance with Investigational Review Board/Independent Ethics Committee (IRB/IEC) requirements
- 5. Subject's caregiver is willing and able to be compliant with diary completion, visit schedule and study drug accountability.
- 6. Subjects must be receiving a therapeutically relevant and stable dose of antiseizure medications, dietary therapies for epilepsy or vagus nerve stimulation settings for at least 4 weeks prior to screening and are expected to remain stable throughout the initial 14 weeks of the study. Medication changes are allowed during the extension portion.
- 7. ≥4 convulsive seizures (tonic-clonic, tonic, atonic, clonic, focal motor) per 4week period; each convulsive seizure must last ≥ 3 seconds.
- 8. Subject is receiving at least 1 concomitant AED and up to 4 concomitant AEDs, inclusive. KD and VNS are permitted but do not count towards the total number of AEDs. Rescue Receiving at least 1 concomitant AED and up to 4 concomitant AEDs, inclusive. Rescue medications for seizures are not counted towards the total number of AEDs.

5.2 Exclusion Criteria

An individual who meets any of the following criteria will be excluded from participation in this study:

- 1. Subject has a known hypersensitivity to fenfluramine or any of the excipients in the study medication.
- 2. Subject has current or past history of cardiovascular or cerebrovascular disease, myocardial infarction or stroke.
- 3. Subject has current or past history of cardiovascular or cerebrovascular disease, such as cardiac valvulopathy, myocardial infarction or stroke, or clinically significant structural cardiac abnormality, including but not limited to mitral valve prolapse, atrial or ventricular septal defects, patent ductus arteriosis, and patent foramen ovale

Version: 11 Jan 2021

with reversal of shunt. (note: Patent foramen ovale or a bicuspid valve are is not considered exclusionary, but may be associated with the following diseases, which are exclusionary: coarctation of the aorta, Turner syndrome, supravalvular aortic stenosis, subvalvular aortic stenosis, patent ductus arteriosus, Sinus of Valsalva aneurysm, ventricular septal defect, Shone's complex, ascending aortic aneurysm, Loeys-Dietz syndrome, ACTA2 mutation familial thoracic aortic aneurysm syndrome, and MAT2A mutation familial thoracic aortic aneurysm syndrome).

- 4. Subject has current or recent history of Anorexia Nervosa, bulimia, or depression within the prior year that required medical treatment or psychological treatment for a duration greater than 1 month.
- 5. Subjects who are currently on formulations of CBD (other than Epidiolex), CBD/THC or any MMJ.
- 6. Subject who have positive urine tetrahydrocannabinol (THC) Panel or whole blood cannabidiol (CBD) who have not been prescribed Epidiolex.
- 7. Subject has participated in another clinical trial within the past 30 days (calculated from that study's last scheduled visit).
- 8. Subject is at imminent risk of self-harm or harm to others, in the investigator's opinion, based on clinical interview.
- 9. Subject has a current or past history of glaucoma.
- 10. Subject is receiving concomitant therapy with: centrally-acting anorectic agents; monoamine-oxidase inhibitors; any centrally-acting compound with clinically appreciable amount of serotonin agonist or antagonist properties, including serotonin reuptake inhibition; atomoxetine, or other centrally-acting noradrenergic agonist; or cyproheptadine. (see appendix 1)
- 11. Subject has moderate or severe hepatic impairment. Asymptomatic subjects with mild hepatic impairment (elevated liver enzymes <3x upper limited of normal [ULN] and/or elevated bilirubin <2x ULN) may be entered into the study after review and approval by the Medical Monitor in conjunction with the sponsor, in consideration of comorbidities and concomitant medications.

5.3 Strategies for Recruitment and Retention

During a routine visit at the NYU Comprehensive Epilepsy Center, subjects who meet criteria for the study (or their parents/legal guardians) will be asked if they would like to participate in the study. Note: some subjects may hear of this study from other parents with CDD or from the International Foundation for CDKL5 Research (https://www.cdkl5.com), which lists studies for patients with CDD. Such subjects who contact the Principal Investigator or research staff will be screened for their potential to participate based on inclusion and exclusion criteria.

Male and female subjects of any ethnicity between ages of 2 and 35 (inclusive) will be

Version: 11 Jan 2021

assessed for inclusion, with no more than 3 patients between the ages of 18-35.

During the routine visit, the investigator will inform each prospective subject/parent/legal guardian of the nature of the study, and explain the potential risks and study-related procedures. If the subject/parent/legal guardian agrees, they will be given the informed consent documents to read and sign prior to starting any study procedures. Only the Principal Investigator, sub-investigators, and other research personnel listed on the study will have access to subject information. Once the study subject/parent/legal guardian has signed the informed consent, the investigator will explain the study during the routine visit. If necessary, the investigator will inform the subject and surrogate that a capacity assessment will be performed to determine whether the subject is capable of providing an informed decision to participate in the study. At this time, a capacity assessment will be conducted if the subject does not refuse the assessment. Capacity will be assessed through neurological examinations and neuropsychology reports conducted by the physician as well as learning and/or development delays that have been documented. If there is already documentation of lack of capacity, no assessment will be needed. If it has been determined by the investigator that the subject has capacity, they will be given the assent form to review. The investigator will go over the study as described in the assent form including study visits and procedures. The subject will be allowed time to ask questions. If the subject is comfortable, then they can sign the assent. All documentation will be placed in the study binder and documented in the study visit note. A copy of the informed assent and consent documents will be given to the subject and the subject's parent/legal guardian. Screening procedures may begin. The Screening Period is 4 weeks, during which study candidates must complete a diary documenting the frequency and duration of seizures.

Refer to Section 7 for the Schedule of Events and specific requirements for each study visit.

5.4 Duration of Study Participation

Subject participation will be a total of 14 weeks with extension available.

5.5 Total Number of Participants and Sites

Approximately 10 patients with a confirmed genetic/clinical diagnosis of CDKL5 Deficiency Disorder (CDD) will be recruited for the study from the Principal Investigator's and co-investigator's clinical practice at New York University Comprehensive Epilepsy Center (NYUCEC) or from families that contact the Principal Investigator. Male and female subjects of any ethnicity between ages of 2 and 35 (inclusive) will be assessed for inclusion, with no more than 3 patients between the ages of 18-35.

5.6 Participant Withdrawal or Termination

5.6.1 Reasons for Withdrawal or Termination

A subject may be discontinued from study drug at any time if the subject, subject's legal guardian, or the investigator feels that it is not in the subject's best interest to continue. The following is a list of possible reasons for study drug discontinuation:

- 1. Parental/legal guardian withdrawal of consent.
- 2. Subject is not compliant with study procedures.

Study number: s18-01530 Page 13 Version: 11 Jan 2021

3. Protocol violation requiring discontinuation of study drug.

- 4. Severe adverse events, including significant toxicity such as severe cognitive or behavioral toxicity, impaired liver and renal function, or impaired hematopoiesis
- 5. Seizure exacerbation not attributable to other known provocative factors.
- 6. Interaction with concomitant AED regimen that leads to unacceptable toxicity. Medication adjustments will be avoided, if possible, and may require the subject to exit the study, at the discretion of the Investigator.

Specific drug-related toxicities will be assessed and managed by the Principal Investigator.

Depending on the nature of the signs (eg, changes in serum chemistries, liver function tests) or symptoms (eg, rash), the subject will be assessed to determine the severity and likelihood of relation to study medication. Based on this assessment, the medication may be discontinued, the dose may be reduced, or the drug may be continued with ongoing assessment. If the study drug is discontinued due to a suspected toxicity, it will only be restarted if there is strong evidence that the toxicity was likely not related to the study medication (eg, liver tests were elevated due to a cytomegalovirus infection).

If a subject must discontinue study drug, the method for discontinuation from study drug will be determined based on the type of reaction and/or reason for withdrawal. For example, if the subject experiences a rapidly progressive rash, it would lead to abrupt cessation of study drug, but if subject experiences excess tiredness, study drug may be tapered off. A discussion of the method of cessation will occur between the subject and/or subject's parent/legal guardian and the physician.

5.6.2 Handling of Participant Withdrawals or Termination

For all subjects who withdraw from the study, there will be 1 final telephone/email follow-up 4 weeks after the last dose of study drug (Post taper Follow-up Visit). If the subject/parent/legal guardian cannot be contacted after 4 phone calls to subject/parent/legal guardian, a certified letter will be sent to the subject/parent/legal guardian.

Refer to Section 7 for the Schedule of Events and specific requirements for each study visit.

5.7 Premature Termination or Suspension of Study

This study may be temporarily suspended or prematurely terminated if there is sufficient reasonable cause. Written notification, documenting the reason for study suspension or termination, will be provided by the suspending or terminating party to Principal investigator. If the study is prematurely terminated or suspended, the PI will promptly inform the IRB and will provide the reason(s) for the termination or suspension.

Circumstances that may warrant termination or suspension include, but are not limited to:

- Determination of unexpected, significant, or unacceptable risk to participants
- Demonstration of efficacy that would warrant stopping
- Insufficient compliance to protocol requirements
- Data that are not sufficiently complete and/or evaluable

CONFIDENTIAL

Version: 11 Jan 2021

Determination of futility

Study may resume once concerns about safety, protocol compliance, data quality is addressed and satisfy the sponsor, IRB and/or FDA.

6 Study Agent

• 0					
Investigational Medicinal Product – ZX008					
Substance Code	ZX008				
Active Substance (INN)	Fenfluramine Hydrochloride				
Trade Name	Not applicable				
Formulation (including dosage form and strength)	Solution 2.5mg/mL				
Route/Mode of Administration	Oral				
Manufacturer	Andersonbrecon, Inc. on behalf of Zogenix International Limited				

6.1 Study Agent Description

ZX008 drug product is an oral aqueous solution of fenfluramine hydrochloride buffered to pH 5 and provided in concentrations of 2.5 mg/mL. The excipients selected have been approved for use in the formulations of currently marketed drug products and are considered to be safe. The solution formulations will be suitably flavored, and will contain preservatives and a thickening agent. The product is sugar free and is intended to be compatible with a ketogenic diet. The doses to be studied will be 0.8 mg/kg/day divided into two daily doses, up to a maximum of 30 mg/day.

6.1.1 Acquisition

The investigational medicinal product (IMP) will be supplied to the study site by the sponsor or its delegate.

All IMP will be transported, received, stored, and handled strictly in accordance with the container or product label, the instructions supplied to the research site and its designated pharmacy, the site's standard operating procedures, and applicable regulations. IMP must be stored separately from normal hospital or practice inventories, in a locked facility with access limited to the investigator and authorized personnel. The investigator must ensure that the IMP is dispensed only to subjects enrolled in this study according to this study protocol.

6.1.2 Formulation, Appearance, Packaging, and Labeling

ZX008 drug product will be provided in a concentration of 2.5 mg/mL in 1 bottle size with nominal fill volume of 120 ml. The ZX008 product will be packaged and labeled according to current International Conference on Harmonization (ICH), Good Manufacturing Practices (GMP), and Good Clinical Practices (GCP) guidelines, and national legal requirements.

Dosing directions for the product can be found in the IMP handling instructions for the study subjects and for the investigator.

6.1.3 Product Storage and Stability

Appropriate storage temperature and transportation conditions will be maintained for the study drug from the point of manufacture up to delivery of the study drug. Study medication must be stored at 15-25°C (59-77°F) with excursions of 5-30°C (41-86°F) permitted; do not

Version: 11 Jan 2021

refrigerate or freeze. Storage and handling instructions of the IMP maintained at the subject's home are described in the subject's IMP handling instructions.

All unused IMP will be saved by the site for final disposition according to the sponsor's directive.

6.1.4 Dosing and Administration

Study medication will be administered as equal doses BID in the morning and in the evening approximately 12 hours apart. Each dose should be separated by a minimum of 8 hours and a maximum of 12 hours.

6.1.5 Route of Administration

Medication is given orally.

6.1.6 Starting Dose and Dose Escalation Schedule

Patients will be titrated over 14 days to a dose of ZX008 0.8 mg/kg/day (maximum dose 30 mg/d).

Titration schedule					
	Day 1-4	Day 5-8	Day 9-14		
	ZX008 0.2	ZX008 0.4	ZX008 0.8		
	mg/kg/day	mg/kg/day	mg/kg/day		

After completion of the Titration Period, subjects will enter the Maintenance Period and continue to receive this dose of ZX008 and be treated for an additional 12 weeks. Study medication will continue to be administered BID in the morning and in the evening, approximately 12 hours apart. Each dose should be separated by a minimum of 8 hours and a maximum of 12 hours. A missed dose of study medication may be taken later up to 8 hours before the next scheduled dose; otherwise, the missed dose should not be given.

6.1.7 Taper Period

Subjects will decrease from 0.8 mg/kg BID to a dose of 0.4 mg/kg BID (maximum 30 mg/day or). After 4 days at this dose level, subjects will decrease their dose to 0.2 mg/kg/day. On Study Day 9, all subjects will stop taking study medication. The taper is expected to take a total of 8 days.

Taper schedule					
	Day 5-8 after end of	Day 9-14 after end of			
	study/ study	study/ study			
	withdrawal	withdrawal			
	ZX008 0.4 mg/kg/day	ZX008 0.2 mg/kg/day			

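### Section 6.1.7: the taper text gives doses as BID where maintenance and the taper table are per day, and text and table disagree on the length of the last step (4 versus 6 days)

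*Combined protocol and SAP*

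**What the plan says.** The maintenance dose is consistent across the dosing sections. Section 6.1 states: "The doses to be studied will be 0.8 mg/kg/day divided into two daily doses, up to a maximum of 30 mg/day". Section 6.1.4 adds: "Study medication will be administered as equal doses BID in the morning and in the evening approximately 12 hours apart". Section 6.1.6 titrates to the same 0.8 mg/kg/day with the same daily maximum.

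The taper in Section 6.1.7 is given twice, in a paragraph and in a table.

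- **Paragraph, first step:** "Subjects will decrease from 0.8 mg/kg BID to a dose of 0.4 mg/kg BID".
- **Paragraph, second step:** "After 4 days at this dose level, subjects will decrease their dose to 0.2 mg/kg/day".
- **Paragraph, end:** "On Study Day 9, all subjects will stop taking study medication. The taper is expected to take a total of 8 days".
- **Table:** "ZX008 0.4 mg/kg/day" on Days 5-8, then 0.2 mg/kg/day in a column whose label begins "Day 9-14 after end of" (study or withdrawal).

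The taper is called on elsewhere. At Visit 5 (Section 7.5.1), subjects who have not responded and will not enter the extension are given it. Section 8.4.3 has subjects who report a pregnancy complete it. Section 5.6.1 leaves the method of stopping to the circumstances of other withdrawals, with tapering as one option.

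**The concern.** The paragraph attaches BID to its first two doses and per day to its third. The first two do not fit the maintenance dose the subject is coming from, or the table below. The paragraph and table also differ on how long the last dose is given.

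This is the protocol's only schedule for withdrawing an antiseizure drug, in people who entered with at least 4 convulsive seizures per 4 weeks (Section 5.1). Site staff have to turn it into instructions for a caregiver measuring an oral solution. As it stands, two staff members could hand out different doses or different stop days and each point to Section 6.1.7 as authority.

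**Working it through.** No sample-size or power figure is involved. The check is arithmetic on doses and days.

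**The plan's own figure.** The text gives 4 days at the first step, a stop on Day 9 and a total of 8 days. The second step is therefore 8 − 4 = 4 days, and 4 + 4 = 8 with the first drug-free day on Day 9. The paragraph's length is consistent with itself.

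**Units.** Daily dose = amount per dose × 2 when given BID.

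- Maintenance (6.1, 6.1.4, 6.1.6): 0.8 mg/kg/day ÷ 2 = 0.4 mg/kg BID.
- Taper text, starting dose: 0.8 × 2 = 1.6 mg/kg/day, and 1.6 / 0.8 = 2 times maintenance.
- Taper text, first step: 0.4 × 2 = 0.8 mg/kg/day, equal to maintenance.
- Taper text, second step: 0.2 mg/kg/day, already per day.
- Table: 0.4, then 0.2 mg/kg/day.

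Reductions from the maintenance dose actually taken:

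- Table, or text with the unit corrected: 1 − 0.4/0.8 = 50%, then 1 − 0.2/0.4 = 50%.
- Worst-case misreading (text followed, table overlooked): 1 − 0.8/0.8 = 0%, then 1 − 0.2/0.8 = 75%. The 75% applies up to 30/0.8 = 37.5 kg, where the 30 mg/day maximum does not limit maintenance.

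At an assumed 20 kg (the protocol gives no weights), maintenance is 16 mg/day. The first step is 16 mg/day as written and 8 mg/day in the table. The second step is 4 mg/day in both.

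**Length of the final step, with the unit corrected.**

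- 0.4 mg/kg/day: 4 days in the text; Days 5-8 = 4 days in the table. These agree.
- 0.2 mg/kg/day: 4 days in the text; Days 9-14 = 6 days in the table. These differ by 2 days.
- Size: 2 × 0.2 = 0.4 mg/kg of additional drug under the table, or 8 mg at the assumed 20 kg.

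This comparison does not depend on where day counting starts. The text appears to count from the start of the taper and the table counts from end of study or withdrawal, but a change of origin cannot turn a 6-day step into a 4-day one. The extracted table shows no column for Days 1-4. One may have been lost in reading the PDF, so nothing is concluded about those days or the table's total length. A recovered column would not remove the difference in the final step.

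**The case against.** The strongest reply is that this is a drafting slip any clinician would see through. The sentence says the dose will decrease, the other dosing sections are in daily totals, the sentence's own last step is per day, and the table directly beneath has the right units. Visit 5 and Section 8.4.3 refer to the taper schedule, which is the table's title, so the table may be what staff use. The program has one site and about 10 patients, Section 5.6.1 allows individual judgment on stopping, and subjects remain on 1 to 4 background antiseizure drugs.

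Much of that stands. The intended unit can be recovered, and the following stronger readings should be resisted:

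- **Subjects would be dosed at 1.6 mg/kg/day.** A reader might infer this, but no section assigns that dose. It appears only as the misstated starting point of the taper.
- **The plan prescribes no reduction and then a 75% drop.** This requires taking the first step literally, replacing the sentence's starting dose with maintenance, and ignoring both the verb and the table. It is a worst-case misreading.
- **The 30 mg/day maximum is misapplied to the reduced dose.** The parenthesis carrying it breaks off mid-phrase and the protocol gives no weights, so nothing can be built on it.

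The reply does not dispose of the length conflict. No other section says whether the last step is 4 or 6 days. The table's day labels match those of the titration table in Section 6.1.6, so they may have been carried over, but the documents do not confirm this. Individual judgment under Section 5.6.1 also does not excuse a written default that contradicts itself.

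**Conclusion.** The point holds as a correction that should be made to a dosing instruction. The BID wording in Section 6.1.7 is wrong against the maintenance dose: as written, the first step is no reduction. Per-day units are very likely intended and agree with the table. Separately, text and table differ by two days at 0.2 mg/kg/day, and the protocol does not resolve this.

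The size is modest. If staff follow the table's doses, what remains is the two-day difference. The 0% then 75% pattern is a risk only if someone follows the sentence alone. The conclusion assumes that the text's second step lasts 4 days, inferred from its Day 9 stop and 8-day total, and that the two printed table columns are read correctly.

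A reader might infer that the efficacy result is at risk. It is not: the taper follows the week-14 assessment. The documents also do not show that the schedule families receive repeats the error, or that a taper two days shorter would cause harm, so neither is claimed.

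**What to change.** In the Section 6.1.7 text, change both BID entries to per day, so that the steps read 0.8 to 0.4 to 0.2 mg/kg/day, and say that each daily total is given in two doses.

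Have the clinical team choose one length for the final step, and number the days in both text and table from the first reduced dose:

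- **Text's length kept:** 0.4 mg/kg/day on taper Days 1-4, 0.2 mg/kg/day on Days 5-8, stop on Day 9.
- **Table's 6-day final step kept:** 0.4 mg/kg/day on taper Days 1-4, 0.2 mg/kg/day on Days 5-10, stop on Day 11 (4 + 6 = 10 dosing days). The text's stop day and total are changed to match.

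Replace the reference to a study day with a taper day. Then check that the written schedule given to families at Visit 5 agrees with the corrected section.

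The cost is an amendment of one section and a check of one handout, with no added procedures or patients.

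### The first taper step in section 6.1.7 does not reliably lower the dose: as worded it equals the maintenance dose, and on the table's units it is no decrease at 75 kg or more

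*Combined protocol and SAP*

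**What the plan says.** **Maintenance dose.** Section 6.1: "The doses to be studied will be 0.8 mg/kg/day divided into two daily doses, up to a maximum of 30 mg/day". Section 6.1.6 agrees: "Patients will be titrated over 14 days to a dose of ZX008 0.8 mg/kg/day (maximum dose 30 mg/d". So 30 mg/day is the ceiling for the full dose.

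**Taper, text of 6.1.7.** "Subjects will decrease from 0.8 mg/kg BID to a dose of 0.4 mg/kg BID (maximum 30 mg/day or"; the parenthesis closes straight after the last word shown. After 4 days the dose falls to 0.2 mg/kg/day, and "On Study Day 9, all subjects will stop taking study medication". The section puts the whole taper at 8 days.

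**Taper, table in 6.1.7.** The first step is "ZX008 0.4 mg/kg/day", on Days 5-8 after the end of study or withdrawal. The second is 0.2 mg/kg/day on Days 9-14. The table shows no maximum.

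**Who tapers.** At Visit 5, patients who do not continue into the extension are given a taper schedule. Section 8.4.3 has a pregnant subject withdraw and complete the taper. Section 6.1.7 is the only schedule printed.

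**Reduced doses and discretion.** Section 2.3.2 (Levels 2 and 3, item 3d) and section 5.6.1 both allow the dose to be lowered during the study. When a subject must stop, section 5.6.1 says "the method for discontinuation from study drug will be determined based on the type of reaction and/or reason for withdrawal". It gives no dose steps.

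**The concern.** The first step of a taper should lower the dose, and 6.1.7 says that it will. Two features of the printed step work against this. The amount is written per administration (BID), while every maintenance dose in the protocol is written per day. The only maximum attached to the step is the one that already applies to the full dose. A caregiver sheet copied from this sentence could hold a patient at full dose for 4 days of an 8-day taper, leaving one real reduction before stopping. Withdrawal for pregnancy is a case where extra days at full dose are unwelcome.

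The section also starts only from full dose. A patient whose dose was lowered for a valve finding or for toxicity has no printed step, and following the sheet literally could hold or raise the dose.

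**Working it through.** **Inputs.** Maintenance is 0.8 mg/kg/day, maximum 30 mg/day (6.1, 6.1.6). Taper step 1 is 0.4 mg/kg BID, maximum 30 mg/day (6.1.7 text), or 0.4 mg/kg/day (6.1.7 table). The documents give no body weights, so the weights W below (in kg) are assumed. The plan prints no worked taper dose to reproduce.

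**Maintenance.** M = min(0.8 × W, 30). The maximum takes effect at 30 / 0.8 = 37.5 kg.

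**Reading 1: the sentence as worded.** Step 1 = min(2 × 0.4 × W, 30) = min(0.8 × W, 30) = M. The first cut is 0% at every weight. The sentence's own starting dose, 0.8 mg/kg BID, would be 1.6 mg/kg/day, which no other section prescribes. BID therefore looks like a slip for a daily dose.

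**Reading 2: the table's unit with the printed maximum.** Step 1 = min(0.4 × W, 30), which reaches 30 mg/day at 30 / 0.4 = 75 kg.

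| Weight (kg) | Maintenance (mg/day) | Step 1 (mg/day) | Change |
|---|---|---|---|
| 20 | 16 | 8 | -50% |
| 37.5 | 30 | 15 | -50% |
| 40 | 30 | 16 | -46.7% |
| 50 | 30 | 20 | -33.3% |
| 60 | 30 | 24 | -20.0% |
| 70 | 30 | 28 | -6.7% |
| 75 | 30 | 30 | 0% |
| 80 | 30 | min(32, 30) = 30 | 0% |

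At 75 kg the second step is 0.2 × 75 = 15 mg/day, so the only reduction before stopping is 30 to 15.

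**Reading 3: the 30 mg/day belongs to the starting dose, so step 1 has no maximum.** Results are unchanged up to 75 kg. Above that the step is an increase: at 80 kg, 0.4 × 80 = 32 mg/day, or 32 / 30 - 1 = +6.7%.

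**If a lower limit L followed the broken phrase.** On reading 2, any L below 30 mg/day restores a decrease at 75 kg and above. On reading 1, L restores a cut only above L / 0.8 kg; with L = 15 that is 18.75 kg.

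**Reduced-dose patients (illustration; the documents state no reduced dose).** Suppose a capped patient was halved to 15 mg/day. Printed step 1 on the table unit is then 15 mg at 37.5 kg (equal), 16 mg at 40 kg (+6.7%) and 20 mg at 50 kg (+33.3%). A 20 kg patient reduced to 8 mg/day would get 0.4 × 20 = 8 mg, no change.

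**Days.** The text gives 4 + 4 = 8 days, with the drug stopped on Day 9. The table gives Days 5-8 (4 days) and Days 9-14 (6 days), 10 dosing days ending on Day 14. On Day 9 the text has the patient off drug and the table has the patient on 0.2 mg/kg/day. A column may have been lost from the table in the copy read here, but that would not remove the Day 9 conflict.

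**The case against.** **The mg/kg ladder is coherent.** A reader might infer that every patient above 37.5 kg is tapered wrongly because the first cut is under 50%. The documents do not support that. No section promises a 50% first cut. The taper retraces the titration in 6.1.6 (0.2, 0.4, 0.8 mg/kg/day under one 30 mg/day maximum), so unequal percentage steps in capped patients are built in going up as well as down. At 50 kg the sequence is 30, 20, 10, 0 mg/day, and each step falls. This objection stands.

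**The sentence is visibly broken.** A second, lower limit may have been lost after the last word, in editing or in reading the file. That is possible, and the 75 kg result depends on its absence. It would not repair the BID unit.

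**Reduced-dose patients are covered by discretion.** A reader might infer that the taper sheet would push such patients back up. Section 6.1.7 is written for patients coming down from full dose and directs no one upward. Section 5.6.1 leaves the method of stopping to discussion with the family, and 2.3.2 gives echocardiogram-related dose decisions to the investigator and cardiologist. This would probably prevent the problem, and the percentages above rest on an assumed dose. What remains is that no section supplies the doses to use.

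**The working instructions are not in the documents.** Section 6.1.2 refers to separate handling instructions, and the sheet handed out at Visit 5 may give individual volumes. That cannot be judged here. The protocol text they should follow still needs to be right.

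**Conclusion.** The point holds as a minor dosing-safety correction. As worded, step 1 equals the maintenance dose at every weight. On the table's daily unit, which matches 6.1 and 6.1.6 and is probably what was intended, step 1 is still no decrease at 75 kg or more. The 75 kg result assumes that no lower limit followed the broken phrase. Between 37.5 and 75 kg the table schedule falls at each step and is acceptable. The reduced-dose gap is real on paper but softened by 5.6.1.

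Reach is small. The study enrols about 10 patients at one site, "with no more than 3 patients between the ages of 18-35" (section 5.5). Weights are not given, so the number at 75 kg or more is unknown and probably small. The unit and day conflicts, by contrast, bear on anyone who tapers by this section. The documents record no harm, and neither the seizure endpoint nor the secondary endpoints are affected.

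**What to change.** Rewrite 6.1.7 as follows:

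- State the steps per day, divided into two doses: 0.4 mg/kg/day, maximum 15 mg/day, for 4 days; then 0.2 mg/kg/day, maximum 7.5 mg/day, for 4 days; then stop. For full-dose patients this equals 50% then 25% of the current daily dose (0.4 × 37.5 = 15; 0.2 × 37.5 = 7.5). The percentage form also covers patients on a reduced dose.
- State that no taper step may equal or exceed the current dose.
- Complete or delete the broken maximum.
- Align the table days (5-8 and 9-14) with the 8-day text.
- Keep the discretion in 5.6.1, including abrupt stopping.

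At the cap this gives 30, 15, 7.5, 0 mg/day. Section 6.1 describes the solution as "provided in concentrations of 2.5 mg/mL", so the volumes are 30 / 2 / 2.5 = 6 mL, 15 / 2 / 2.5 = 3 mL and 7.5 / 2 / 2.5 = 1.5 mL, each twice a day. At 37.5 kg or less, full-dose patients get the same doses as the existing table.

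The cost is one amended paragraph with its table, a revised caregiver sheet and a per-patient calculation when the taper starts. No visits or procedures are added. The trade-off is a steeper first cut for capped patients between 37.5 and 75 kg: 50% instead of, for example, 33.3% at 50 kg. If the sponsor prefers to keep the gentler ladder in that range, correcting the unit and the days and adding the rule on the current dose would still remove the fault, provided a dose below 30 mg/day is named for step 1 at 75 kg or more.
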